### Disease activity (at Day 1)

- For CD patients: Harvey Bradshaw Index (HBI) score or Crohn's Disease Activity Index (CDAI);
- For UC patients: 9-item partial Mayo Score (always collected) and the total Mayo score (when available).

The Harvey Bradshaw Index (HBI) score considers five easily assessed dimensions (general wellbeing, abdominal pain, number of liquid stools per day, abdominal mass, and complications). These dimensions are scored from the previous day (no diary cards are required). Patients with HBI  $\geq 8$  are classified as presenting moderate to severe active disease (22).

The Crohn's Disease Activity Index (CDAI) evaluates the severity of signs and symptoms of CD. Collected data include information on the number of liquid stools, intensity of abdominal pain, general well-being, presence of comorbid conditions, use of medications for diarrhea, physical examination, and laboratory findings (abdominal mass, hematocrit, body weight), yielding 8 items that are combined with data from a 7-day diary to obtain the total CDAI score. Higher scores indicate a greater disease severity. Moderate to severe active CD is defined as  $CDAI \ge 220$  (23).

The Maxo score is composed of four categories (bleeding, stool frequency, physician assessment, and endoscopic appearance) rated from 0-3 that are summed to give a total score that ranges from 0-12. The partial Mayo Score (pMayo) was previously compared with the full Mayo score and categorizes patients as being in remission (score of 0-2), having mild disease (pMayo of 3 or 4) or moderate to severe disease (pMayo of  $\geq$ 5) (24).

Health-Related Quality of Life and Work Productivity (at Day 1)

- 36-item Short Form Health Survey (SF-36)
- 5-dimensional EuroQoL measure (EQ-5D)
- Inflammatory Bowel Disease Questionnaire (IBDQ) 32 items
- Work Productivity and Activity Impairment Questionnaire (WPAI) 6 items

le terms of Use The Short Form-36 (SF-36) evaluates 8 health dimensions: physical functioning, bodily pain, role physical (limitations due to physical problems), role emotional (limitations due to personal or emotional problems), mental health, social functioning, vitality, and general health perceptions. Based on these 8 scales, two weighted scores are generated: the physical component summary (PCS) and the mental component summary (MCS) score. Scores range between 0 and 100, with higher scores indicating a better quality of life (25). For additional information, please consult

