### 5 PROTOCOL CLARIFICATIONS

The last secondary objective, estimation of healthcare resources cost, will not be calculated as stayed in section 3 of the protocol (3. Study objectives), since these variables were not The of Use collected in the CRF.

Adverse events were not collected in the study database and results regarding these variables will not be presented in the statistical report.

Secondary endpoint "Proportion of patients who guit their job due to IBD and have not been able to return to work" will not be calculated as stayed in section 10.1.1 of the protocol (10.1.1 Study endpoints), since these variables were not collected in the CRF

In the protocol the analysis dataset was not defined. In this SAP the analysis dataset was defined according to section 6 Definition of analysis subsets.

The descriptive analysis for continuous variables will be summarized by mean, standard variation, median, maximum, minimum as stayed in the protocol and also by first quartile and third quartile.

## 6

DEFINITION OF ANALYSIS SUBSETS only and Analysis dataset - All patients fulfilling selection criteria (section 4), who provided the written informed consent, without major study protocol deviations and who have completed the Day 1 assessment will be included in the statistical analysis dataset.

### RATIONALE AND CALCULATION OF THE SAMPLE SIZE 7

It is expected to include 246 patients regardless of IBD type.

This sample size will allow estimates with 95% confidence interval and a margin of error less than 5%, and assuming a rate of inadequate control of disease of 20% (conservative approach), regardless of IBD type. The following formula was used:

$$n = \frac{1.96^2 \times p \times (1-p)}{ME^2}$$

Rate of uncontrolled disease (p) = 20%

Margin of error (ME) = 0.05

Expected recruitment period: 6 months

ofUse

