## 8 STATISTICAL METHODS

For each study endpoint, data will be summarized for total IBD patients and by IBD type (CD and UC).

Statistical analysis will allow a characterization of the study population, the estimation of primary endpoints and to compare the subgroup of patients with mild or no activity of disease and those with moderate to severe activity. A descriptive analysis will be obtained for all relevant variables, with absolute and relative frequency for categorical variables and mean, standard variation, median, maximum, minimum, first quartile and third quartile, for continuous ones. For each study endpoint, data will be summarized by IBD type (CD or UC). Hence, for each IBD type, the patients with disease activity will be compared with patients with mild or no activity regarding socio-demographic, clinical and treatment variables of interest. The variable normality assumption will be tested using the Kolmogorov-Smirnov test or Shapiro-Wilk test as applicable. Non-parametric tests will be used whenever the assumptions for parametric tests are not accepted. Chi-square or Fisher exact tests will be used to compare activity vs non-activity regarding qualitative variables and t-student / Mann-Whitney tests will be used for comparison of quantitative variables. If applicable, logistic regression will be used for evaluating associated variables. Variables with clinical significance or statistical significance (p<0.200) will be included in the initial logistic regression model, or otherwise specified by the sponsor. All tests will be two-sided considering a significance level of 5%.

Data analysis will be performed using SAS® (version 9.4; SAS Institute Inc, Cary, USA).

There will be no imputation of missing data for this study, unless otherwise specified.

In case of complete missing dates, date is to be considered as missing.

In case of partial dates:

Missing day is to be considered as the 15th day of the month;

• Missing day and month are to be considered as the 1st day of July.

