### **Secondary Analyses** 8.2

The following objectives will be addressed for all IBD patients:

- In order to characterize socio-demographic and clinical aspects of moderate to severe IBD, a summary table with the descriptive statistics of the selected variables, by CD and UC patients.
- Descriptive statistics will also be used to summarize treatment patterns for CD and UC in the previous 3 years, including the use of biologic therapies and failure to these therapies (if any), time between IBD diagnosis and initial treatment, first treatment after diagnosis of moderate to severe IBD, among other variables of interest.
- Within CD and UC groups, the patients with moderate to severe disease activity will be compared with patients with mild or no activity, regarding socio-demographic, clinical and treatment variables of interest:
  - o Chi-square or Fisher exact tests will be used to compare qualitative variables, such as gender, smoking habits, professional status, family history of IBD, steroid behavior (dependent/refractory), previous treatment with biologic therapies, and previous surgery for IBD, among others.
  - The t-student or Mann-Whitney tests will be used for comparison of quantitative variables, such as age, time since diagnosis, and duration of treatment, among others.

 $\infty$  If applicable, logistic regression models (for CD and UC patients) will be used to identify independent variables associated with disease control at Day 1, and odds ratios (OR) with 95% CI will be presented.

For each IBD disease, a descriptive statistical analysis will be used to summarize patients' QoL (Quality of Life), overall and according to disease activity

• The score of EQ-5D analog scale and responses to each item (Mobility, Selfcare, Usual activity, Pain/discomfort, Anxiety/depression):

- Utilities will be configured such that 0 is associated with being dead and 100 is associated with perfect health; thus, a higher utility value is considered better. Mean (SD) utility index will be estimated for CD and UC patients, overall and according to disease activity.

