- The SF-36 uses 36 items to evaluate eight health dimensions (Physical functioning, Role Physical, Body pain, General health, Vitality, Social Functioning, Role-Emotional, Mental Health) and based on standardized scores, two summary scores are to be estimated (Physical Component Score and Mental Component Score). The standard scoring method for SF-36 questionnaire will be obtained using the QualityMetric Health Outcomes™ Scoring Software 4.5 provided by QualityMetric Incorporated.
- The IBDQ score and each of the four IBDQ domains (Bowel systems, Emotional health, Systematic systems and Social function). Total IBDQ score range from 32 to 224, with a higher score reflecting better quality of life. Response to each of the questions is graded from 1 to 7 ("1" being the worst situation and "7" the best). Please see section 9. *Data, derivations and transformations* for the IBDQ scores calculation. Note: The IBDQ is not validated for patients with ostomies and therefore should not be applied for these patients.
- The comparison of SF 36 scale scores or component summary scores, EQ-5D VAS scale and IBDQ domain scores or total score according to disease activity will be performed through the t-test for independent samples or Mann-Whitney test in case of non-normality of the quantitative variable distribution. The association between each EQ-5D dimension and disease activity will be determined for each IBD type using Chi-Square Test.

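### In UC, quality of life and work impairment are related to disease activity only through the active/not-active cut; a supplementary analysis on the partial Mayo score already collected would be a cheap gain in power

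*SAP*

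**What the plan says.** SAP 8.2 compares SF-36, EQ-5D VAS and IBDQ scores between patients with and without active disease: the comparison "according to disease activity will be performed through the t-test for independent samples or Mann-Whitney test". The four WPAI percentages get the same two-group tests, and each EQ-5D dimension gets a chi-square test against activity. For other variables, SAP 8 states that "Chi-square or Fisher exact tests will be used to compare activity vs non-activity regarding qualitative variables", and SAP 8.2 adds, if applicable, that "logistic regression models (for CD and UC patients) will be used to identify independent variables associated with disease control at Day 1". SAP 8 also states: "All tests will be two-sided considering a significance level of 5" per cent.

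Activity is defined by partial Mayo of 5 or more in UC, and by HBI of 8 or more or CDAI of 220 or more in CD. SAP 9 derives the Day 1 scores only as cut-offs. The three-level HBI/CDAI variable is labelled back to moderate-to-severe or no/mild.

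For UC, Protocol 7.2 lists the "9-item partial Mayo Score (always collected"), and distinguishes remission (0-2), mild disease (3-4) and moderate to severe disease (5 or more). In CD the site records HBI or CDAI.

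One secondary objective (SAP 2.1.2) does ask for active patients to be compared with the rest, but only on socio-demographic, clinical and treatment variables. The quality-of-life and WPAI objectives do not mention the cut.

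**The concern.** For IBDQ, SF-36, EQ-5D VAS and WPAI, the two-group contrast is an analysis choice and not something the objectives require. It pools a UC patient at partial Mayo 4 with one at 0, and a patient at 5 with one at 9. The gradient between remission and mild disease, which the protocol itself describes, enters no planned test.

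At the planning rate the split is also uneven, about one active patient to four not active. If quality of life or work loss changes steadily with the score, a two-group test on that split uses much less of the data than a test on the score. A modest association could then be reported as not significant although the data on file would support it.

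**Working it through.** **Inputs from the documents.** SAP 7: "It is expected to include 246 patients regardless of IBD type"; "Rate of uncontrolled disease (p) = 20" per cent; "Margin of error (ME) = 0.05". SAP 8: two-sided tests at 5%.

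**The plan's own figure.** n = 1.96² × 0.20 × 0.80 / 0.05² = 245.86, rounded up to 246. It reproduces. It is a precision calculation for one proportion. The documents give no power or effect size for any association, so there is no power figure to reproduce.

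**Assumptions not in the documents.** An even CD/UC split, giving 123 UC patients; a linear association of size r between score and outcome; a normal model for the formula. At 20% active, 123 patients divide into 24.6 active and 98.4 not active.

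**Information kept by the cut.** Cutting a normal variable so that a share p lies above the cut multiplies the correlation by φ(z)/√(p(1−p)).
- p = 0.20: 0.280/0.400 = 0.700, squared 0.49.
- p = 0.40: 0.386/0.490 = 0.789, squared 0.62.

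This step needs neither r nor the sample size.

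**Power by the normal formula, shown at r = 0.25, N = 123, 20% active.**
- Score kept: atanh(0.25) × √120 = 0.2554 × 10.954 = 2.798; Φ(2.798 − 1.96) = 79.9%.
- Cut: attenuated correlation 0.25 × 0.700 = 0.175; mean difference 0.175/0.400 = 0.437; within-group SD √(1 − 0.175²) = 0.985; standard error 0.985 × √(1/24.6 + 1/98.4) = 0.222; ratio 1.971; Φ(1.971 − 1.96) = 50.4%.

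| r | Score, % | Cut, % | Loss, points |
|---|---|---|---|
| 0.10 | 19.5 | 11.9 | 7.6 |
| 0.15 | 38.0 | 21.5 | 16.5 |
| 0.20 | 60.3 | 34.8 | 25.5 |
| 0.25 | 79.9 | 50.4 | 29.5 |
| 0.30 | 92.4 | 66.3 | 26.0 |
| 0.40 | 99.6 | 89.9 | 9.8 |
| 0.50 | 100.0 | 98.5 | 1.4 |

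**Simulation.** With an integer 0-9 score, 20% of patients at 5 or above and N = 123, the t-test on the cut against Spearman on the score gives 35% vs 55% at r = 0.20, 48% vs 74% at 0.25 and 64% vs 88% at 0.30. These are losses of 20, 26 and 24 points. The loss is about 13 points at r = 0.15, about 11 at 0.40 and 2 at 0.50. Both tests reject near 5% under the null.

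**Sensitivity (normal formula, except the step effect).**
- 40% active: losses of 12, 18, 19 and 15 points at r = 0.15, 0.20, 0.25 and 0.30.
- Other numbers of UC patients, 20% active: the peak loss stays at 29 to 30 points but moves, to about r = 0.35 at N = 62 and about r = 0.21 at N = 184.
- Step effect at the cut-off, r = 0.25, N = 123 (simulated): the t-test on the cut has 78% power against 59% for Pearson correlation on the score. The ranking reverses.

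**CD.** HBI and CDAI cannot be pooled as numbers, whereas the binary variable does combine them. Suppose about half of 123 CD patients have HBI (N = 62). The HBI analysis then has 34.4%, 50.1% and 66.2% power at r = 0.20, 0.25 and 0.30. The cut on all 123 has 34.8%, 50.4% and 66.3%. The gain is nil.

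**The case against.** The strongest reply is that the cut is the question asked. A secondary objective names the contrast between moderate-to-severe and no-or-mild activity, and the endpoints give the cut-offs. A per-point trend answers something different. This stands for socio-demographic, clinical and treatment variables, so nothing specified should be dropped or demoted. It does not cover the quality-of-life and WPAI objectives, which are silent on the cut.

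A reader might infer that the plan loses a fixed 15 to 26 points of power in every association analysis. The documents do not support that. The figure needs an r, a UC sample size and a linear effect that they do not give, and depending on those the loss runs from about 0 to 30 points or reverses. The 20% rate is itself a planning value, and Protocol 6.2 expects patients with active disease to attend more often, which would make the split less uneven.

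A reader might also infer that real links with quality of life will often be missed. That is not shown either. The activity indices and IBDQ both cover bowel symptoms, so strong correlations are plausible (an inference; no r is given), and at r = 0.40 the cut already has about 90% power.

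Two further points stand. Protocol 6.2 calls the objectives mainly descriptive and Protocol 10.5 calls all analyses descriptive, so no power target is breached. Protocol 10.1 commits to describing all collected data, and the table shells are an external document, so the raw scores may well be tabulated. The gap concerns tests of association only. Against this, SAP 8 does set 5% tests, so their efficiency is a fair question.

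**Conclusion.** The point holds as a cheap improvement, mainly for UC quality-of-life and WPAI outcomes. The assumption-light part is that a 20:80 cut keeps about 49% of the information on a linear association, and a 40:60 cut about 62%. The power loss is conditional on 123 UC patients, 20% active and linearity: about 13 to 26 points by simulation, or 16 to 30 by the normal formula, at r = 0.15 to 0.30; about 10 at r = 0.40; 2 or fewer at r = 0.50. Under a true step at the cut-off the specified analysis is the better one, which is a reason to report both. In CD no gain is shown, because the mix of HBI and CDAI is not given. The primary proportions are unaffected, and the specified comparisons are not in error.

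**What to change.** Leave every active versus not-active comparison as specified. In SAP 8.2 add for UC a prespecified supplementary analysis of IBDQ, SF-36, EQ-5D VAS and WPAI on the Day 1 partial Mayo score, by Spearman correlation or linear regression, naming which. Optionally add a proportional-odds model of the score beside the binary logistic model. In CD, report the same associations separately for HBI and for CDAI, as descriptive support only.

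The cost is a few lines of SAP text and some additional SAS procedures on data already collected; no new patients, visits or variables are needed. The downsides are one more set of tables, more unadjusted tests, and a per-point effect that does not translate directly into an odds ratio for active disease. Label the additions as supplementary so that they are not read as replacing the specified contrast.

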## 9 DATA, DERIVATIONS AND TRANSFORMATIONS

Analysis dataset: A dichotomous variable (yes/no) will be calculated.

- Yes Patients who meet all inclusion criteria, not meet any of the exclusion criteria, sign the informed consent, without major study protocol deviations and who have completed the Day 1 visit.
- No Otherwise

Age at Day 1 (years): The difference between the Day 1 date and the patient's birth date, in years.

cable terms of Use Moderate to severe Crohn's disease (active CD disease): A dichotomous variable (yes/no) will be calculated.

Yes – Patients with HBI score  $\geq$  8 or CDAI score  $\geq$  220 at Day 1 visit.

No - otherwise.

Moderate to severe Ulcerative Colitis disease (active UC disease): A dichotomous Yes – Patients with 9-point partial Mayo score  $\geq$  5 at Day 1. variable (yes/no) will be calculated.

id subject

Time since IBD diagnosis and Day 1(years) - time between the IBD diagnosis and Day 1 visit, in years.

Time since first treatment after IBD diagnosis and Day 1 (years) - time between the start date of first IBD treatment after diagnosis and date of Day 1 visit, in years.

Time since diagnosis of moderate to severe IBD and Day 1 (years) - time between the date of moderate to severe IBD and date of Day 1 visit, in years.

Time Since first treatment (or treatment change) after moderate to severe IBD diagnosis and Day 1 (years) - time between the start date of first IBD treatment/treatment change after moderate to severe diagnosis and date of Day 1 visit, in years.

**BMI** - The following formula must be considered:  $\frac{Weight(Kg)}{Height(m)^2}$ 

Terms of Use

BMI categories – The BMI will be recoded according to the following cut-offs:

Underweight – BMI <18.50 kg/m^2

Normal range – BMI between 18.50 and 24.99 kg/m^2

Overweight – BMI between 25.00 and 29.99 kg/m^2

Obese – BMI  $\ge$  30.00 kg/m^2

**Total number of extra intestinal manifestation conditions per patient** – Sum of all of extra intestinal manifestation conditions by each patient in the previous 3 years

**Total number of not extra intestinal manifestation conditions per patient** – Sum of all not extra intestinal manifestation conditions by each patient in the previous 3 years.

Harvey Bradshaw Index cut-off - A dichotomous variable will be calculated:

HBI score  $\geq$  8 points – Patients with Harvey Bradshaw Index equal or higher than 8 points.

HBI score < 8 points – Patients with Harvey Bradshaw Index lower than 8 points.

Crohn's Disease Activity Index cut-off - A dichotomous variable will be calculated:

CDAI score  $\ge$  220 points – Patients with Crohn's Disease Activity Index equal or higher than 220 points.

CDAI score < 220 points – Patients with Crohn's Disease Activity Index lower than 220 points.

HBI and CDAI cut-offs - A trichotomous variable will be calculated:

→ HBI score ≥ 8 points and CDAI score ≥ 220 points (Moderate to severe) – Patients with HBI equal or higher than 8 points and CDAI equal or higher than 220 points.

HBI score < 8 points and CDAI score < 220 points (No or mild) – Patients with HBI lower than 8 points or CDAI lower than 220 points.

15 of USE

HBI score < 8 points and CDAI score > 220 points OR HBI score > 8 points and CDAI score < 220 points (Moderate to severe) – Patients with HBI lower than 8 points and CDAI equal or higher than 220 points OR patients with HBI equal or higher than 8 points and CDAI lower than 220 points.

Patients with only HBI score assessed at Day 1 - A dichotomous variable (yes/no) will be calculated.

Yes – Patients with HBI score assessed at Day 1 and without CDAI score assessed at Day 1.

No – Patients with HBI score and CDAI score evaluated at Day 1 and patients with only CDAI score evaluation at Day 1.

Patients with missing information in both scores will be considered as a missing value in this new variable.

Patients with only CDAI score assessed at Day - A dichotomous variable (yes/no) will be calculated.

Yes – Patients with CDAI score assessed at Day 1 and without HBI score assessed at Day 1.

No – Patients with HBI score and CDAI score evaluated at Day 1 **and** patients with only HBI score evaluation at Day 1.

Patients with missing information in both scores will be considered as a missing value in this new variable.

Patients with HBI score and CDAI score assessed at Day 1 - A dichotomous variable (yes/no) will be calculated.

Yes – Patients with CDAI score and HBI score assessed at Day 1.

No – Patients with only one score (CDAI or HBI) assessed at Day 1.

Patients with missing information in both scores will be considered as a missing value in this new variable.

HBI score and CDAI score not assessed at Day 1 - A dichotomous variable (yes/no) will be calculated:

Yes – Patients without CDAI score and without HBI score assessments at Day 1.

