# Secondary Endpoints:

- Distribution of age, gender, smoking habits, professional status, family history, educational level, subject income by IBD type.
- Distribution of clinical variables (steroid behaviour, anthropometric information, medical history and comorbidities, clinical characterization of disease) by IBD type.
- Therapies for IBD (aminosalicylates, steroids, immunomodulators, immunosupressors biologics, antibiotics, probiotics and surgeries) and the length of these therapies during the previous 3 years.

0

is of Use

- Proportion of biologic-experienced patients.
- Proportion of patients who have not responded previously to biologic therapies and reason.
- IBD treatment introduced at Day 1 (if applicable).
- Socio-demographic, clinical and treatment-related variables in patients with moderate to severe activity of CD (HBI  $\geq$  8 or CDAI  $\geq$  220 points) versus patients with mild or no activity (HBI < 8 or CDAI < 220 points).
- Socio-demographic, clinical and treatment-related variables in patients with moderate to severe activity of UC (partial Mayo score  $\geq$ 5) versus patients with mild or no activity (partial Mayo <5).
- Mean score of EQ-5D by IBD type.
- Mean score of different components of SF-36 by IBD type.
- Mean total score of IBDQ and by domain (bowel symptoms, systemic symptoms, emotional function and social function). Patients with ostomy will not be evaluated since this questionnaire only and subi is not validated to be used in this population.
- Mean total percentage of work impairment (WPAI). •
- Mean work time missed (WPAI).
- Mean impairment while working (WPAI). •
- Mean total activity impairment (WPAI). •
- Proportion of patients who quit their job due to IBD and have not been able to return to work. •
- Healthcare resources (previous 3 years): drug therapies, imaging and laboratory testing, surgeries, hospitalizations and consultations.

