### 2.2.2 Secondary endpoints

- Distribution of age, gender, smoking habits, professional status, family history, educational level, subject income by IBD type.
- Distribution of clinical variables (steroid behaviour, anthropometric information, medical history and comorbidities, clinical characterization of disease) by BD type.
- Therapies for IBD (aminosalicylates, steroids, immunomodulators, immunosupressors biologics, antibiotics, probiotics and surgeries) and the length of these therapies during the previous 3 years. Property of Taked

Proportion of biologic-experienced patients.

Proportion of patients who have not responded previously to biologic therapies and reason.

- IBD treatment introduced at Day 1 (if applicable).
- Socio-demographic, clinical and treatment-related variables in patients with moderate to severe activity of CD (HBI score  $\geq$  8 or CDAI score  $\geq$  220 points) versus patients with mild or no activity (HBI score < 8 or CDAI score < 220 points).

- Socio-demographic, clinical and treatment-related variables in patients with moderate to severe activity of UC (9-point partial Mayo score ≥5) versus patients with mild or no activity (9-point partial Mayo score <5).
- Mean score of EQ-5D by IBD type.
- Mean score of different components of SF-36 by IBD type.
- Mean total score of IBDQ and by domain (bowel symptoms, systemic symptoms, emotional function and social function). Patients with ostomy will a in the applicable not be evaluated since this questionnaire is not validated to be used in this population.
- Mean total percentage of work impairment (WPAI).
- Mean work time missed (WPAI).
- Mean impairment while working (WPAI).
- Mean total activity impairment (WPAI).
- Healthcare resources (previous 3 years): drug therapies, imaging and laboratory testing, surgeries, hospitalizations and consultations. y and sul

### STUDY DESIGN 3

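### SAP section 9: the no-or-mild level of the three-level HBI/CDAI variable is labelled with *and* but defined with *or*, and the active-CD flag counts patients with neither index as not active

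*SAP*

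**What the plan says.** SAP section 9 contains two derivations that combine the indices.

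- **Active-CD flag** ("active CD disease): A dichotomous variable (yes/no) will be calculated"). *Yes* if HBI is at least 8 or CDAI is at least 220 at Day 1; *No* for everyone else.
- **Three-level HBI/CDAI variable.** One level needs both indices at or above their cut-offs. The second is labelled "HBI score < 8 points and CDAI score < 220 points (No or mild", but its defining text reads "Patients with HBI lower than 8 points or CDAI lower than 220 points". The third holds the discordant patients, for example "Patients with HBI lower than 8 points and CDAI equal or higher than 220 points", and is labelled moderate to severe.

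The same section expects that some patients will have both indices (a flag for "Patients with CDAI score and HBI score assessed at Day 1") and that some may have neither ("Patients without CDAI score and without HBI score assessments at Day 1").

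The comparison endpoint also uses *or* on its lower side. SAP 2.2.2 has "patients with mild or no activity (HBI score < 8 or CDAI score < 220 points", and the secondary endpoints in the protocol summary have "patients with mild or no activity (HBI < 8 or CDAI < 220 points". SAP 2.2.1 ties the choice of index to the criteria of the site.

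SAP 8.1 divides the active CD patients by all CD patients. SAP section 6 admits to the analysis set patients who completed Day 1, without saying that this requires an activity index. SAP 8.2 compares moderate-to-severe with mild-or-no-activity patients but does not name the grouping variable.

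**The concern.** A derived variable must give each patient at most one value. The defining text of the no-or-mild level does not do this for a CD patient with, say, HBI 9 and CDAI 200. The patient satisfies that text because CDAI is low, and also satisfies the discordant level. The *or* also treats patients with one index unevenly: a low score is enough to enter no-or-mild, but a high score reaches no level, because the other two levels need both scores. A table built from the text would then mix populations and over-fill its no-or-mild row.

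The residual *No* in the active-CD flag is a separate problem of missing data. A CD patient with no index at Day 1 has unknown activity, yet is recorded as not active. That is in effect an imputation, whereas SAP section 8 plans none unless otherwise specified. This flag defines the primary endpoint, so here the primary CD proportion is exposed.

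**Working it through.** **1. Cases against the written rules.** A dash means not assessed.

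| HBI | CDAI | Active-CD flag | No-or-mild by label (*and*) | No-or-mild by text (*or*) | Discordant level | Both-high level |
|---|---|---|---|---|---|---|
| 5 | 150 | No | yes | yes | no | no |
| 5 | 300 | Yes | no | **yes** | **yes** | no |
| 10 | 150 | Yes | no | **yes** | **yes** | no |
| 10 | 300 | Yes | no | no | no | yes |
| 5 | – | No | no | **yes** | no | no |
| – | 150 | No | no | **yes** | no | no |
| 10 | – | Yes | no | no | no | no |
| – | 300 | Yes | no | no | no | no |
| – | – | **No** | no | no | no | no |

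By the text, both discordant rows take two levels, low single-index rows enter no-or-mild, and high single-index rows take none. By the label, the levels are exclusive and cover exactly the patients with both indices. The flag is single-valued in every row, and its only doubtful entry is the last.

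**2. Inputs for size.** The planned total reproduces: 1.96² × 0.20 × 0.80 / 0.05² = 245.86, so 246. The documents do not give the CD count, the share with both indices (s) or the discordance rate among them (d). All are assumed:

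- CD count N: 246 × 0.123 = 30.3, using the CD share of the local study cited in the protocol Introduction, up to 246 / 2 = 123.
- s: 10% to 50%. It may be low, because CDAI needs a 7-day diary (protocol 7.2).
- d: 5% to 20%.

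**3. Discordant patients = N × s × d.**

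- Smallest: 30.3 × 0.10 × 0.05 = 0.15.
- Largest: 123 × 0.50 × 0.20 = 12.3.
- At N = 123, s = 10%, d = 10%: 1.2.

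**4. Illustration of the three-level variable coded from its text.** Take N = 123, s = 50%, d = 10% and 20% active on each index. The 20% borrows the overall planning rate and is not index-specific. Of 61.5 patients with both indices:

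- discordant: 61.5 × 0.10 = 6.15
- both high: 61.5 × (0.20 − 0.05) = 9.2
- both low: 61.5 − 6.15 − 9.2 = 46.1

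Of 61.5 with one index, 61.5 × 0.80 = 49.2 are low and 61.5 × 0.20 = 12.3 are high. The text gives a no-or-mild level of 46.1 + 6.15 + 49.2 = 101.5, against 46.1 by the label, and leaves 12.3 patients without a level. Against all exclusively no-or-mild CD patients (46.1 + 49.2 = 95.3), the discordant patients add 6.15 / 95.3 = 6.5%. With d = 20% this becomes 12.3 / 92.25 = 13%; with s = 10% and d = 5% it is 0.6 / 98.1 = 0.6%.

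**5. Neither index.** If a share m of CD patients has no index and p is the active proportion among those assessed, the reported proportion is p × (1 − m). With p = 20% (planning rate):

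- one patient in 123: 20% × (1 − 1/123) = 19.8%
- m = 5%: 19.0%
- m = 10%: 18.0%

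The values of m are assumptions; m may be zero.

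**The case against.** The strongest reply is that the SAP already settles discordance. The active-CD flag makes a patient active on either index and is exclusive by construction; the *and* label and the moderate-to-severe label on the discordant level agree with it. That stands, and it is why this is a drafting error and not an open question about which index governs.

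A reader might go further and infer that the *or* in SAP 2.2.2 and the protocol endpoint puts discordant patients on both sides of the CD comparisons, so that the two-sample tests and logistic models are invalid. The documents do not support this. Since the index follows the site's criteria, the *or* there can fairly mean whichever index the site used, with the same index on both sides. The active-CD flag is also the only two-level variable in the visible SAP that combines both indices, so it is the evident grouping variable, and a three-level variable cannot directly feed a two-sample test. The table shells are an external document, not available here, and may name it.

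The site-criteria reading cannot rescue the three-level variable, because its other two levels need both scores. Nor does the reply touch patients with neither index.

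**Conclusion.** The point holds as a minor one, in two parts.

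First, the defining text of the no-or-mild level contradicts its own label, overlaps the discordant level and handles single-index patients unevenly. The error is confined to the three-level variable. A reader might infer that it shifts the primary CD proportion; it does not, because the flag's rule for discordant patients is unambiguous.

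Second, the residual *No* of the flag would lower the primary CD proportion if CD patients without any index are in the analysis set. The SAP foresees such patients and does not clearly exclude them.

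The number affected cannot be derived from the documents. Discordant patients and patients with neither index may each be about one or none. The 6.5% and 13% figures, and the 101.5 against 46.1, are illustrations on assumed rates and not estimates of bias. The textual conflict is certain; its practical effect may be negligible.

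**What to change.** 1. **Three-level variable (SAP section 9).** Change the no-or-mild text to *and*, and state that the variable is derived only for patients with both indices at Day 1.
2. **Active-CD flag (SAP section 9).** Set *No* only when at least one index was assessed and every assessed index is below its cut-off. Set the flag to missing when neither was assessed. A plain *and* would not do here, because it would drop patients with one index. State in SAP 8.1 how patients with a missing flag count in the denominator: if all CD patients still form it, setting the flag to missing leaves the proportion unchanged. Report their number.
3. **SAP 8.2.** Cite this flag as the grouping variable for the CD activity comparisons.
4. **Optional.** Add a note in SAP section 5 on what *or* means in the comparison endpoint. The protocol need not be amended for this.

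The cost is a few sentences in the SAP and a check that the external table shells agree. No new data are needed. If programming has started, SAP section 1 already provides for documenting such changes in the Statistical Report.
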